### **7.2.1 Definition of an Overdose for This Protocol and Reporting of Overdose to the Sponsor-Investigator and to Merck**

For purposes of this trial, an overdose of pembrolizumab will be defined as any dose of 1,000 mg or greater ( $\geq 5$  times the indicated dose). No specific information is available on the treatment of overdose of pembrolizumab. Appropriate supportive treatment should be provided if clinically indicated. In the event of overdose, the subject should be observed closely for signs of toxicity. Appropriate supportive treatment should be provided if clinically indicated.

If an adverse event(s) is associated with ("results from") the overdose of a Merck product, the adverse event(s) is reported as a serious adverse event, even if no other seriousness criteria are met.

If a dose of Merck's product meeting the protocol definition of overdose is taken without any associated clinical symptoms or abnormal laboratory results, the overdose is reported as a non-serious Event of Clinical Interest (ECI), using the terminology "accidental or intentional overdose without adverse effect."

9458- Protocol Version Date 28 Feb 2019

All reports of overdose with and without an adverse event must be reported within 24 hours to the Sponsor-Investigator and within 2 working days hours to Merck Global Safety. (Attn: Worldwide Product Safety; [contact])

## **7.2.2 Reporting of Pregnancy and Lactation to the PI and to Merck**

Although pregnancy and infant exposure during breast feeding are not considered adverse events, it is the responsibility of investigators or their designees to report any pregnancy or lactation in a participant (spontaneously reported to them) that occurs during the study.

Pregnancies and infant exposures during breastfeeding that occur after the consent form is signed but before treatment allocation/randomization must be reported by the investigator if they cause the participant to be excluded from the trial, or are the result of a protocol-specified intervention, including but not limited to washout or discontinuation of usual therapy, diet, placebo treatment or a procedure.

Pregnancies and infant exposures during breastfeeding that occur from the time of treatment allocation/randomization through 120 days following cessation of Sponsor's product, or 30 days following cessation of treatment if the participant initiates new anticancer therapy, whichever is earlier, must be reported by the investigator. All reported pregnancies must be followed to the completion/termination of the pregnancy. Pregnancy outcomes of spontaneous abortion, missed abortion, benign hydatidiform mole, blighted ovum, fetal death, intrauterine death, miscarriage and stillbirth must be reported as serious events (Important Medical Events). If the pregnancy continues to term, the outcome (health of infant) must also be reported.

Such events must be reported within 24 hours to the Sponsor and within 2 working days to Merck Global Safety. (Attn: Worldwide Product Safety; [contact])

## **7.2.3 Immediate Reporting of Adverse Events to the PI and to Merck**

### **7.2.3.1 Serious Adverse Events**

A serious adverse event is any adverse event occurring at any dose or during any use of pembrolizumab that:

- Results in death;
- Is life threatening;
- Results in persistent or significant disability/incapacity;
- Results in or prolongs an existing inpatient hospitalization;
- Is a congenital anomaly/birth defect;
- Is a new cancer (that is not a condition of the study);
- Is associated with an overdose;
- Is another important medical event

Refer to Table 6 for additional details regarding each of the above criteria.

For the time period beginning when the consent form is signed until treatment allocation/randomization, any serious adverse event, or follow up to a serious adverse event,

9458- Protocol Version Date 28 Feb 2019

including death due to any cause that occurs to any participant must be reported within 24 hours to the Sponsor and within 2 working days to Merck Global Safety if it causes the participant to be excluded from the trial, or is the result of a protocol-specified intervention, including but not limited to washout or discontinuation of usual therapy, diet, placebo treatment or a procedure.

For the time period beginning at treatment allocation/randomization through 90 days following cessation of treatment, or 30 days following cessation of treatment if the participant initiates new anticancer therapy, whichever is earlier, any serious adverse event, or follow up to a serious adverse event, including death due to any cause whether or not related to the Merck product, must be reported within 24 hours to the Sponsor and within 2 working days to Merck Global Safety.

Additionally, any serious adverse event, considered by an investigator who is a qualified physician to be related to Merck product that is brought to the attention of the investigator at any time following consent through the end of the specified safety follow-up period specified in the paragraph above, or at any time outside of the time period specified in the previous paragraph also must be reported immediately to Merck Global Safety.

All participants with serious adverse events must be followed up for outcome.

**SAE reports and any other relevant safety information are to be forwarded to the Merck Global Safety [contact]**

A copy of all 15 Day Reports and Annual Progress Reports is submitted as required by FDA, European Union (EU), Pharmaceutical and Medical Devices agency (PMDA) or other local regulators. Investigators will cross reference this submission according to local regulations to the Merck Investigational Compound Number (IND, CSA, etc.) at the time of submission. Additionally investigators will submit a copy of these reports to Merck & Co., Inc. (Attn: Worldwide Product Safety; [contact]) at the time of submission to FDA.

### **7.2.3.2 Events of Clinical Interest**

Selected non-serious and serious adverse events are also known as Events of Clinical Interest (ECI) and must be reported within 2 working days to Merck Global Safety. (Attn: Worldwide Product Safety; [contact]).

For the time period beginning when the consent form is signed until treatment allocation/randomization, any ECI, or follow up to an ECI, that occurs to any participant must be reported within 2 working days to Merck Global Safety if it causes the participant to be excluded from the trial, or is the result of a protocol-specified intervention, including but not limited to washout or discontinuation of usual therapy, diet, placebo treatment or a procedure.

For the time period beginning at treatment allocation/randomization through 90 days following cessation of treatment, or 30 days following cessation of treatment if the participant initiates new anticancer therapy, whichever is earlier, any ECI, or follow up to an ECI, whether or not related to Merck product, must be reported within 2 working days to Merck Global Safety.

9458- Protocol Version Date 28 Feb 2019

1. an overdose of Merck product, as defined in Section 7.2.1 - Definition of an Overdose for This Protocol and Reporting of Overdose to the Sponsor-Investigator, that is not associated with clinical symptoms or abnormal laboratory results.
2. an elevated AST or ALT lab value that is greater than or equal to 3X the upper limit of normal and an elevated total bilirubin lab value that is greater than or equal to 2X the upper limit of normal and, at the same time, an alkaline phosphatase lab value that is less than 2X the upper limit of normal, as determined by way of protocol-specified laboratory testing or unscheduled laboratory testing.\*

\*Note: These criteria are based upon available regulatory guidance documents. The purpose of the criteria is to specify a threshold of abnormal hepatic tests that may require an additional evaluation for an underlying etiology. The trial site guidance for assessment and follow up of these criteria can be found in the Investigator Trial File Binder (or equivalent).

#### **7.2.4 Evaluating Adverse Events**

An investigator who is a qualified physician will evaluate all adverse events according to the most current available version of NCI Common Terminology for Adverse Events (CTCAE). Any adverse event which changes CTCAE grade over the course of a given episode will have each change of grade recorded on the adverse event case report forms/worksheets.

All adverse events regardless of CTCAE grade must also be evaluated for seriousness.

9458- Protocol Version Date 28 Feb 2019

Table 6: Evaluating Adverse Events

An investigator, who is a qualified physician, will evaluate all adverse events as to:

CTCAE Grading	Grade 1	Mild; asymptomatic or mild symptoms; clinical or diagnostic observations only; intervention not indicated.
	Grade 2	Moderate; minimal, local or noninvasive intervention indicated; limiting age-appropriate instrumental ADL.
	Grade 3	Severe or medically significant but not immediately life-threatening; hospitalization or prolongation of hospitalization indicated; disabling; limiting self-care ADL.
	Grade 4	Life threatening consequences; urgent intervention indicated.
	Grade 5	Death related to AE
Seriousness	A serious adverse event is any adverse event occurring at any dose or during any use of Merck product that:	
	†Results in death; or	
	†Is life threatening; or places the subject, in the view of the investigator, at immediate risk of death from the event as it occurred (Note: This does not include an adverse event that, had it occurred in a more severe form, might have caused death.); or	
	†Results in a persistent or significant disability/incapacity (substantial disruption of one's ability to conduct normal life functions); or	
	†Results in or prolongs an existing inpatient hospitalization (hospitalization is defined as an inpatient admission, regardless of length of stay, even if the hospitalization is a precautionary measure for continued observation. (Note: Hospitalization [including hospitalization for an elective procedure] for a preexisting condition which has not worsened does not constitute a serious adverse event.); or	
	†Is a congenital anomaly/birth defect (in offspring of subject taking the product regardless of time to diagnosis); or	
	Is a new cancer; (that is not a condition of the study) or	
	Is an overdose (whether accidental or intentional). Any adverse event associated with an overdose is considered a serious adverse event. An overdose that is not associated with an adverse event is considered a non-serious event of clinical interest and must be reported within 24 hours.	
	Other important medical events that may not result in death, not be life threatening, or not require hospitalization may be considered a serious adverse event when, based upon appropriate medical judgment, the event may jeopardize the subject and may require medical or surgical intervention to prevent one of the outcomes listed previously (designated above by a †).	
Duration	Record the start and stop dates of the adverse event. If less than 1 day, indicate the appropriate length of time and units	
Action taken	Did the adverse event cause the Merck product to be discontinued?	
Relationship to test drug	Did the Merck product cause the adverse event? The determination of the likelihood that the Merck product caused the adverse event will be provided by an investigator who is a qualified physician. The investigator's signed/dated initials on the source document or worksheet that supports the causality noted on the AE form, ensures that a medically qualified assessment of causality was done. This initialed document must be retained for the required regulatory time frame. The criteria below are intended as reference guidelines to assist the investigator in assessing the likelihood of a relationship between the test drug and the adverse event based upon the available information.	
	The following components are to be used to assess the relationship between the Merck product and the AE; the greater the correlation with the components and their respective elements (in number and/or intensity), the more likely the Merck product caused the adverse event (AE):	
	Exposure	Is there evidence that the subject was actually exposed to the Merck product such as: reliable history, acceptable compliance assessment (pill count, diary, etc.), expected pharmacologic effect, or measurement of drug/metabolite in bodily specimen?
	Time Course	Did the AE follow in a reasonable temporal sequence from administration of the Merck product? Is the time of onset of the AE compatible with a drug-induced effect (applies to trials with investigational medicinal product)?
	Likely Cause	Is the AE not reasonably explained by another etiology such as underlying disease, other drug(s)/vaccine(s), or other host or environmental factors

9458- Protocol Version Date 28 Feb 2019

Relationship to Merck product (continued)	The following components are to be used to assess the relationship between the test drug and the AE: (continued)	
	Dechallenge	
Was the Merck product discontinued or dose/exposure/frequency reduced?                      If yes, did the AE resolve or improve?                      If yes, this is a positive dechallenge. If no, this is a negative dechallenge.                      (Note: This criterion is not applicable if: (1) the AE resulted in death or permanent disability; (2) the AE resolved/improved despite continuation of the Merck product; or (3) the trial is a single-dose drug trial); or (4) Merck product(s) is/are only used one time.)

	Rechallenge	
Was the subject re-exposed to the Merck product in this study?                      If yes, did the AE recur or worsen?                      If yes, this is a positive rechallenge. If no, this is a negative rechallenge.                      (Note: This criterion is not applicable if: (1) the initial AE resulted in death or permanent disability, or (2) the trial is a single-dose drug trial); or (3) Merck product(s) is/are used only one time).                      NOTE: IF A RECHALLENGE IS PLANNED FOR AN ADVERSE EVENT WHICH WAS SERIOUS AND WHICH MAY HAVE BEEN CAUSED BY THE MERCK PRODUCT, OR IF REEXPOSURE TO THE MERCK PRODUCT POSES ADDITIONAL POTENTIAL SIGNIFICANT RISK TO THE SUBJECT, THEN THE RECHALLENGE MUST BE APPROVED IN ADVANCE BY THE U.S. CLINICAL MONITOR AS PER DOSE MODIFICATION GUIDELINES IN THE PROTOCOL.

	Consistency with Trial Treatment Profile	
Is the clinical/pathological presentation of the AE consistent with previous knowledge regarding the Merck product or drug class pharmacology or toxicology?

The assessment of relationship will be reported on the case report forms /worksheets by an investigator who is a qualified physician according to his/her best clinical judgment, including consideration of the above elements.
		
Record one of the following	Use the following scale of criteria as guidance (not all criteria must be present to be indicative of a Merck product relationship).	
Yes, there is a reasonable possibility of Merck product relationship.	
There is evidence of exposure to the Merck product. The temporal sequence of the AE onset relative to the administration of the Merck product is reasonable. The AE is more likely explained by the Merck product than by another cause.
	
No, there is not a reasonable possibility Merck product relationship	
Subject did not receive the Merck product OR temporal sequence of the AE onset relative to administration of the Merck product is not reasonable OR there is another obvious cause of the AE. (Also entered for a subject with overdose without an associated AE.)
	

## 8.0 DATA AND SAFETY MONITORING PLAN

Institutional support of trial monitoring will be in accordance with the Fred Hutch /University of Washington Cancer Consortium Institutional Data and Safety Monitoring Plan. Under the provisions of this plan, Fred Hutch Clinical Research Support coordinates data and compliance monitoring conducted by consultants, contract research organizations, or Fred Hutch employees unaffiliated with the conduct of the study. Independent monitoring visits occur at specified intervals determined by the assessed risk level of the study and the findings of previous visits per the institutional DSMP.

In addition, protocols are reviewed at least annually and as needed by the Consortium Data and Safety Monitoring Committee (DSMC), Fred Hutch Scientific Review Committee (SRC) and the Fred Hutch /University of Washington Cancer Consortium Institutional Review Board (IRB). The review committees evaluate accrual, adverse events, stopping rules, and adherence to the applicable data and safety monitoring plan for studies actively enrolling or treating patients. The IRB reviews the study progress and safety information to assess continued acceptability of the risk-benefit ratio for human subjects. Approval of committees as applicable is necessary to continue the study.

The trial will comply with the standard guidelines set forth by these regulatory committees and other institutional, state and federal guidelines.

## 9.0 STATISTICAL ANALYSIS PLAN

### 9.1 Statistical Analysis Plan Summary

The primary objective of this study is to evaluate the efficacy of pembrolizumab in MRD-positive ALL. To address this, a Simon two-stage minimax design will be used.

### 9.2 Statistical Analysis Plan

The primary endpoint of this phase II study will be the rate of complete MRD response, defined as the percentage of evaluable subjects who achieve a complete MRD response, as defined in Section 11.3. The study of blinatumomab for chemorefractory MRD cited previously assumed an historical rate of complete MRD response to standard chemotherapy of 5%. Considering the fact that the current study will enroll patients that have previously received or are ineligible for treatment with blinatumomab, we feel it is reasonable to assume a similar historical rate of complete MRD response for subjects in this trial. The design will be based on Simon's two-stage minimax design with an historical response rate of 5% and an assumed-true response rate of 20% for patients receiving treatment on this protocol. The design also assumed a 10% type-I error rate and a 20% type-II error rate. Under these assumptions and parameters, the first stage will enroll 12 evaluable patients. If 0 responses are seen among these 12, the study will be paused for futility to consider alternative strategies to improve efficacy versus consideration of study closure (the probability of 0 responses among 12 under the alternative hypothesis of 20% response is 0.07). On the other hand, if at least 1 response is seen among the first 12 patients, an additional 9 will be enrolled for a total of 21. If at least 3 responses occur among the 21 (14.3% or more), this will be considered as sufficient evidence to conclude that the observed response rate is statistically better than the fixed historical rate of 5%. This yields a type-I error rate of .08 and power of 80% along with an expected sample size of 16.1.

Additionally, the study will be stopped early if there is a signal of unacceptably-high early morphologic relapse. For this stopping rule, the rate of morphologic relapse within the first 2 cycles of treatment will be assessed in cohorts of 5 for the first 15 patients enrolled. If the lower bound of the 80% confidence

interval of the morphologic relapse rate exceeds 50% at these assessments (i.e.,  $\geq 4$  out of 5,  $\geq 7$  out of 10, and  $\geq 10$  out of 15), the study will close early.

Reporting of secondary endpoints, including toxicity profiles, OS, and impact of biomarkers, will be primarily descriptive.

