### **4.2 Rationale**

#### **4.2.1 Rationale for the Trial and Selected Subject Population**

ALL is among the most common forms of cancer in children, and in this circumstance it is highly curable. However, treatment of ALL in adults is very challenging, and outcomes with standard approaches remain unsatisfactory. Apart from the use of ABL kinase inhibitors for patients with the Philadelphia chromosome (t[9;22], abbreviated Ph+), the treatment still relies primarily upon remission induction with intensive multiagent cytotoxic chemotherapy. This is a particular challenge in older adults diagnosed with ALL, as these regimens are (in general) prohibitively toxic for these patients. Therefore, improvements in the treatment of ALL in adults are critically needed.

The importance of MRD in ALL is firmly established. MRD is typically assessed by two different techniques: multiparameter flow cytometry (MFC) to detect the unique abnormal immunophenotype of the leukemic blasts, or polymerase chain reaction (PCR) for clonal DNA alterations (including immunoglobulin or T-cell receptor gene rearrangements or oncogenic chromosomal rearrangements like BCR-ABL). It is understood that the presence of MRD (either as persistence during therapy or reappearance afterward) confers a poor prognosis, as it almost inevitably heralds frank hematologic relapse without additional intervention. Our center's experience also demonstrates the risk associated with MRD in the context of HCT. Its presence is associated with a significantly higher risk of relapse when detected before or after myeloablative HCT. Qualitatively comparable results have been observed from patients undergoing nonmyeloablative conditioning, which may be the only option for HCT in older or medically-infirm patients ([name], personal communication). Unfortunately, for those that have MRD, little is known about the optimal management of this high-risk scenario. However, it stands to reason that elimination of MRD could significantly improve their outcome.

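### Do the stated type-I error, power and expected sample size need revising because they leave out the early-relapse closure rule?

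*Combined protocol and SAP*

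**What the plan says.** Section 9.2 builds the primary analysis on "Simon's two-stage minimax design with an historical response rate of 5% and an assumed-true response rate of 20" per cent, and adds: "The design also assumed a 10% type-I error rate and a 20% type-II error rate". Twelve evaluable patients enter the first stage. With no responses among them the study is paused, and the choice is then between a changed strategy and closure. With at least one response, nine more are enrolled, and three or more responses among 21 count as success. Directly after that success criterion the section prints its operating characteristics: "This yields a type-I error rate of .08 and power of 80% along with an expected sample size of 16.1".

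A new paragraph then begins: "Additionally, the study will be stopped early if there is a signal of unacceptably-high early morphologic relapse". Under it, "the rate of morphologic relapse within the first 2 cycles of treatment will be assessed in cohorts of 5 for the first 15 patients enrolled". The study closes if the lower limit of an 80% confidence "interval of the morphologic relapse rate exceeds 50% at these assessments", and the section lists the triggering counts: at least 4 of 5, 7 of 10 or 10 of 15. It gives no assumed early-relapse rate and no closure probability.

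**The concern.** Both rules apply to the same patients, and a study closed for relapse never reaches the test of three responses in 21. A drug with the target 20% response rate can therefore fail for a reason that the printed power does not count. If early relapse is common, the chance of declaring such a drug active could be well below 80%.

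The background gives some reason to ask. Section 4.2.1 says of residual disease that "it almost inevitably heralds frank hematologic relapse without additional intervention". Section 8.0 gives oversight bodies a role: "The review committees evaluate accrual, adverse events, stopping rules, and adherence to the applicable data and safety monitoring plan". Yet the documents offer those bodies no operating characteristics for this rule. The interval method behind the 80% limit is not named either.

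**Working it through.** **Inputs from section 9.2.** Response rates 5% (null) and 20% (target); pause at 0 of 12; success at 3 or more of 21; relapse closure at 4 or more of 5, 7 or more of 10, 10 or more of 15.

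**Step 1: reproduce the printed figures, Simon rule alone.** The printed 16.1 treats the pause at 0 of 12 as a stop. On that basis

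P(success) = P(X₂₁ ≥ 3) − P(X₁₂ = 0) × P(X₉ ≥ 3), with X binomial.

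- At 5%: 0.0849 − 0.5404 × 0.0084 = 0.0804 (printed .08).
- At 20%: 0.8213 − 0.0687 × 0.2618 = 0.8033 (printed 80%).
- Expected sample size at 5%: 12 + 9 × (1 − 0.5404) = 16.14 (printed 16.1).

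All three agree, so the printed figures are those of the Simon rule without the relapse rule.

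**Step 2: add the relapse rule.** The documents give no early-relapse rate. I assume q, the share of all patients who relapse within two cycles, between 20% and 50%. Each patient is a responder (probability p), an early relapser (q) or neither (1 − p − q). Treating the first two as mutually exclusive is reasonable because section 7.1.2.6 takes relapsed subjects off study. Enrolled and evaluable patients are taken as the same, and two-cycle status as known at each look. An exact patient-by-patient recursion on the counts of responses and relapses then applies both rules.

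| q | Closure for relapse, p = 20% | Power | Loss from 80.3%, points | Type-I error, p = 5% | Expected N, p = 5% |
|---|---|---|---|---|---|
| 20% | 0.7% | 79.9% | 0.5 | 0.080 | 16.1 |
| 30% | 3.6% | 78.0% | 2.4 | 0.079 | 15.8 |
| 40% | 11.8% | 72.6% | 7.7 | 0.075 | 15.1 |
| 50% | 28.7% | 60.8% | 19.5 | 0.067 | 13.8 |

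At q = 50% the first look alone closes the study with probability P(at least 4 of 5) = 6/32 = 18.8%, about two thirds of the 28.7%.

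**Step 3: vary the assumptions.**

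- *The pause does not end the trial.* Power for the Simon rule alone is 82.1%. With the relapse rule it is 81.6%, 79.6%, 73.9% and 61.6% at q = 20%, 30%, 40% and 50%. Without the relapse rule, type-I error is 0.085, still under the 10% limit.
- *The rate applies to non-responders only.* Rates of 20%, 30%, 40% and 50% equal 16%, 24%, 32% and 40% of all patients (multiply by 0.8). Power is 80.1%, 79.4%, 77.3% and 72.6%.
- *Response and early relapse are independent.* Power is 79.8%, 77.4%, 70.7% and 56.9%.

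**Step 4: the interval method.** Lower limits at 4/5, 7/10 and 10/15 are 57.1%, 51.4% and 51.1% by a two-sided 80% Wald interval, and 51.0%, 51.6% and 52.4% by a one-sided 80% exact bound. Both exceed 50% at every listed count. With one relapse fewer (3/5, 6/10, 9/15) the Wald limits are 31.9%, 40.1% and 43.8%, so the counts are the correct thresholds for that method. A two-sided exact interval (41.6%, 44.8%, 46.8%) would not give them. As the counts are written out, the rule can be applied without knowing the method.

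**The case for a change.** The strongest case for a change is that two mandatory rules sit in one section and the reader is given the properties of only one. At 40% early relapse the type-II error is 27% and at 50% it is 39%, against a design allowance of 20%. Fifty per cent is the rule's own threshold, so that end of the range is not fanciful, and section 4.2.1 does not exclude it. A label on the three figures and one small table would cost no patients.

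The arithmetic stands, and so does the observation that no closure probability is given. The rest carries less weight. The printed figures follow the Simon success criterion, while the relapse rule comes in its own paragraph as an addition; nothing claims that the 80% covers both. The large losses need rates the documents do not supply: at 20% response, 40% and 50% of all patients mean 50% (0.40/0.80) and 62.5% (0.50/0.80) of non-responders in morphologic relapse within two 21-day cycles. Section 4.2.1 gives neither a rate nor a time frame. At such rates closure is the protection the rule was written to give, and whether to count it as lost power for the response endpoint is a reporting choice. Nor is 80% a strict ceiling on power, because the first-stage outcome is a pause: if accrual resumes, power at 20% early relapse is 81.6%.

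**Conclusion.** No change to the plan follows. The figures .08, 80% and 16.1 are correct for the design they describe. With both rules, and the pause taken as a stop, power stays within 2.4 points of 80.3% up to 30% early relapse among all patients. It drops by 7.7 points at 40% and 19.5 points at 50%, rates the documents neither support nor exclude. On the same basis, .08 remains a valid bound on the type-I error and the expected sample size can only fall.

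What is missing is descriptive detail. A statistician reporting to the oversight committees can derive the closure probabilities from the listed counts, as above, over whatever relapse rates are thought plausible. Doing so would leave both sets of stopping counts, the success criterion and the analysis as they are. The power figures rest on the assumed range for q, on response and early relapse being mutually exclusive, and on complete two-cycle data at each look.
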